3.3 Study procedures

The recruitment period will presumably start in August 2023 and the latest follow-up visit for a participant is expected to be in December/January 2023. For an individual participant, the recruitment period will be 1 month or shorter and includes an online screening procedure and phone call with Frau [name] or her team. Participants will be informed about all study details as described in 3.2 via email and time will be given to them to make a decision about the participation and to give informed consent at all times. In case of any questions, they can reach out to the person in charge of recruitment via phone. After successful completion of the screening, a first visit at the Dermatology clinic Hautwerk in Zurich will be scheduled as soon as possible (not later than a month). The participants will receive an online medical questionnaire (via REDcap), which they can fill out at home before the first visit if they are able to, or if not they will fill it out at the first visit under supervision of a medical professional (doctor). At the first visit [name] will go through all the relevant information again with the participants which allows them to give their informed consent and will fill out the informed consent form with them. The participants receive a copy of the signed form.

At the first visit at the Dermatology clinic Hautwerk (time point 0), the medical professional will then check if the participant has already filled out the medical questionnaire. If yes, they will go through the most important points to check the participant understood everything correctly, if no, they will supervise the participant in filling out the questionnaire. After the questionnaire is completed, the medical professional will instruct the participant to take a saliva sample via spitting on a spoon and transferring the saliva to a piece of paper (provided by TruMe laboratories). The paper has to dry for 45 minutes in the open air (taken care of by the medical professional). Then, the medical professional performs the non-invasive skin scan (Visia analysis system), and the tests with the corneometer, cutometer and ultrascan. Afterwards, there will be time for the participant to rest until it can be sure that there are no adverse reactions to any of the procedures performed. The whole visit will be recorded by the medical professional. The total visit should take between 30 to 60 minutes. The saliva samples are stored without risk at ambient temperature. The study personnel will collectively ship the samples to Trume labs once all the baseline visits are completed.

Specifics to the skin measurement procedures:

- Cutometer: The cutometer is a non-invasive device that measures the elasticity of the skin. It uses suction to apply a negative pressure on the skin, which causes the skin to deform. The device then measures the time it takes for the skin to return to its original position after the suction is released. This measurement is known as the skin's viscoelastic properties, and it is used to assess the skin's firmness and elasticity.
- 2. Corneometer: Corneometer is a non-invasive device that measures the moisture content of the skin. It works by applying a small electrical current to the surface of the skin, which measures the skin's electrical impedance. The device then calculates the moisture content of the skin based on the electrical impedance. This measurement is used to assess the hydration level of the skin.

- 3. Ultrascan: Ultrascan is a non-invasive device that uses high-frequency ultrasound waves (22 Mhz) to measure the thickness and density of the skin. The device works by emitting ultrasound waves into the skin, which bounce back and are recorded by the device. The time it takes for the ultrasound waves to bounce back is used to calculate the thickness of the skin. This measurement is used to assess the overall health of the skin and collagen content can be read out by it.
- 4. Visia scan: Visia scan is a non-invasive imaging system that captures high-resolution images of the skin's surface. The device uses different types of light, such as UV, polarized, and non-polarized light, to capture images of the skin at different depths. The images are then analyzed to assess various skin conditions, including pigmentation, wrinkles, texture, UV-spots, pores, redness, and porphyrins. This measurement is used to assess the overall health and quality of the skin.

At the time points +1, +2, +3, +4 +5 and +6 months of the study duration, a short online questionnaire will be sent to all participants via email, with a secure link to the REDcap online form. It will contain questions about the product intake (how many days of the months), the health status (any changes, physical or mental illness, adverse reactions), important lifestyle changes, and if the participants are still willing to continue with the study. There will also be the possibility for the participants to reach out to a medical professional or to schedule a visit.

At the timepoints +1 and +3, follow-up visits at the Dermatology clinic Hautwerk will be scheduled (time frame +/- 1 week of the +1 and +3 months time point respectively). The visit will contain the same procedures as the visit at time point 0, minus the saliva sample. The medical professional will again first check the completion of the questionnaire and assist if necessary, then take the skin scan (Visia analysis system), and the tests with the corneometer, cutometer and ultrascan. The participants have then time to rest to make sure there are no adverse reactions to any of the procedures. At time point +3, the participant will be provided with the saliva collection kit for timepoint +6 months. Each visit will be recorded by the medical professional. The total visit should take between 30 to 60 minutes.

At the time point +6 months, a second saliva sample will be collected (time frame +/- 1 week of the +6 months time point). Participants will have received the collection kit at time point +3 by the study personnel. They will be reminded 1 week prior to the due date of the test and 1 day before, and will be informed about the exact procedures on how to perform the test and have the possibility to ask any questions to the study personnel via phone. They have to spit on a spoon and put the saliva on the provided paper and let it air dry for 45 minutes, before sending it to the investigators site (Avea Life, [name]). There the samples will be collectively sent for analysis to Trume labs once all samples from time point +6 have been collected. Storage of the samples is without risk at ambient temperature.

To minimize bias in the study population, during the recruitment process a focus will lie on individual participant attributes that could confound the data like gender, ethnicity and age and there will be efforts made to generate a broad spectrum of study participants to avoid only collecting information from one subgroup of the population. Also, all tests (saliva, skin analyses), and questionnaires are performed on all study participants and for the same duration of time. In the questionnaire we will ask for potential confounders so that we can account for them in the data analysis (e.g. being sick during study period, major changes in behavior etc.). The skin analyses will all be performed by the same person (doctor) to reduce measurement bias.

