2.3 Project design

The study is a human research study in which customers that are taking the collagen activator from Avea are observed for six months. The trial is in the form of a post marketing surveillance observational trial since the product has already been approved and is sold on the market. All participants are voluntarily taking the collagen activator. There is no blinding, randomization or placebo control that is taking place in the trial. The results are compared individually for each participant after the follow ups from their baseline measurements.

- The trial exposure is the Collagen activator from Avea
 - Potential participants are contacted after purchasing the collagen activator for 6 months via Avea's online shop. After successful recruitment they undergo the baseline assessment. They are instructed to only start taking the collagen activator once the baseline assessment is completed.
 - o Daily oral intake of 1 package of 11.5g diluted in water over six months, taken in the morning
- Saliva samples are taken twice (time points 0 and +6 months) to determine biological age via epigenetic methylation clock (Trume labs are the test providers and analysers)
- Skin analysis takes place at time points 0, +1 and +3 months to determine skin quality. This includes measurements of hydration, elasticity, skin thickness and density, as well as pigmentation, wrinkles, texture, UV-spots, pores, redness and porphyrins.
- Skin tests used for this are the corneometer, cutometer, ultrascan and Visia scan.
- Every month the participants receive a questionnaire regarding recent subjective changes, adverse reactions and adherence

The individual duration expected for each patient from the recruitment process onwards is about 6-7 months

- The goal is to recruit 60 healthy participants that are older than 35 years and are voluntarily taking the collagen activator for 6 months
- 2-3 weeks from being recruited to receiving a date for the baseline measurements
- Day 1 being the day of the baseline measurements
- Follow ups for the skin measurements take place +1 and +3 months from day 1
- Follow up for the saliva test takes place +6 months from day 1

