6.2 Risk-Benefit Assessment

The benefits for participants of the projects are the following:

Participants in this study stand to benefit by receiving information about their biological age and their skin quality, which has the potential to improve their welfare and health awareness. These benefits are not only valuable to participants in the short term, but could also have important long-term health implications. By providing participants with free valuable health information, the study team is helping to promote participant welfare and ensure that the project is conducted in an ethical and responsible manner. There are only minimal risks associated with the intervention participants are exposed to and procedures included in this project. They are addressed in the following section together with the risk minimization:

Avea collagen activator (exposure)

• As of now there are no known adverse reactions associated with the product from any of the early trials and since the product has been on the market, there have been no reports of major adverse effects or reactions.

Skin analysis (Corneometer, cutometer, ultrascan (22Mhz), Visia scan

- Risk minimisation during the recruitment process through screening for any sensitivity regarding exposure to light (sunlight, UV-light etc.)
- A medical professional is accompanying the trial participant during that process and on the lookout for any adverse reactions or complications during the process
- All procedures that are part of the skin analysis are non-invasive. In rare cases they can lead to skin irritation or damage, specifically if they are used too often or with too much pressure, which our study personal will be instructed to avoid.
- All skin tests will not be performed on open wounds or skin infections.

Saliva collection

- The risks are minimized as the sample collection is non-invasive (participant spits on a clean spoon).
- The sample collection is self-administered and participants will be provided with clear and concise instructions on how to collect their saliva sample.

Analysis of saliva samples to determine biological age

- The saliva samples are collectively shipped every week (the samples that are ready) to our collaborator, Trume labs, without risk to the samples as they are stable up to one year under ambient conditions.
- For the analysis, 9 small DNA regions are sequenced, and used to determine the methylation of your DNA. Genetic information is not analyzed.

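### At months +1 and +3 the unblinded doctor handles the questionnaire on subjective change and intake before taking the skin readings, and using one assessor does not remove that assessor's expectation

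*Protocol*

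**What the plan says.** Section 2.3 of the protocol states: "There is no blinding, randomization or placebo control that is taking place in the trial". Each participant is compared with their own baseline. The same section describes the questionnaire: "Every month the participants receive a questionnaire regarding recent subjective changes, adverse reactions and adherence". Section 3.3 adds that the form asks on how many days of the month the product was taken, and about health status, lifestyle changes and willingness to continue.

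For the follow-up visits section 3.3 says "The visit will contain the same procedures as the visit at time point 0, minus the saliva sample", and then gives the order: "The medical professional will again first check the completion of the questionnaire and assist if necessary, then take the skin scan". The corneometer, cutometer and ultrascan readings follow. For a questionnaire already completed at visit 0, the same section says of the medical professional: "If yes, they will go through the most important points to check the participant understood everything correctly".

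The safeguard offered for the skin readings, also in section 3.3, is: "The skin analyses will all be performed by the same person (doctor) to reduce measurement bias". The protocol describes no masked reading, does not separate the person who handles the questionnaire from the person who measures, and has no rule on whether earlier readings are visible. Section 7.2 says only that readouts may first be held in the clinic's internal systems before transfer.

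**The concern.** The person who measures the skin also handles the form on which the participant reports how they feel and how regularly they took the product, and does so just before measuring. Someone who has learned that a participant feels improved and took the product every day may, without intending it, place a probe differently or accept a favourable reading more readily.

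Using one doctor keeps differences between assessors out of the data. It leaves that doctor's own expectation untouched. A shift that arises only at follow-up does not cancel in a before-after difference, and with no control group nothing else in the data can reveal it. At stake is the secondary objective in section 2.1, which claims significant improvement in skin quality after 3 months.

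**Working it through.** The plan states no figure on this point, so the main check sets the passages side by side.

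1. **Who measures.** In section 3.3 the medical professional who checks the questionnaire is the grammatical subject that then takes the readings. The same section says one doctor performs all skin analyses. The two roles therefore fall to one person.
2. **What that person may learn.** The follow-up text prescribes a check of completion, with help if needed. Where help is given, the answers are seen. Where it is not, fuller review follows only by carrying over the visit 0 step through "The visit will contain the same procedures as the visit at time point 0, minus the saliva sample". Exposure is certain for some participants, likely for others, and nowhere prevented.
3. **What the form contains.** Subjective change and adherence come from section 2.3, and days of intake from section 3.3.
4. **Which outcomes are exposed.** The corneometer and cutometer are the clearest cases, because an operator applies them. Visia outcomes come from images that are later analysed, with no analyst or method named, so exposure there is open. The biological-age result comes from an external laboratory, so the primary endpoint is outside this point.

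**Illustration of sensitivity to a systematic shift.** Inputs are n = 50 (the section 4.1 size before allowance for drop-out), one-sided alpha 0.05 (section 4.1), and the paired structure that section 4.1 keeps for secondary endpoints. The shift b, in SDs of the paired difference, is an assumption. With no true effect:

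rejection rate = P(T > t(0.95; n − 1)), where T is noncentral t with n − 1 degrees of freedom and noncentrality b√n. For n = 50, √n = 7.071.

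| b | b√50 | rate, n = 50 | rate, n = 60 |
|---|---|---|---|
| 0 | 0 | 0.050 | 0.050 |
| 0.05 | 0.354 | 0.097 | 0.103 |
| 0.10 | 0.707 | 0.172 | 0.190 |
| 0.20 | 1.414 | 0.401 | 0.455 |
| 0.30 | 2.121 | 0.673 | 0.743 |

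These rates are per test, before the Benjamini-Hochberg adjustment named in section 4.1. They show how a single-arm before-after comparison responds to any uniform shift, whatever its source. They do not estimate what visit order contributes.

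**The case against.** The strongest reply is that mechanism and harm do not match well. What a questionnaire reveals is individual: a participant who reports no change, or poor intake, would push expectation the other way. A shift of the same sign for everyone would come mainly from the doctor knowing that it is a follow-up visit and that all participants take the product. Reordering leaves that knowledge in place. This stands, and it limits what the change can achieve. It does not remove the benefit of withholding individual information that the doctor does not need before measuring.

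Several stronger readings are tempting, and the documents do not support them:

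- A reader might infer that the doctor reviews every participant's answers at follow-up. The text prescribes only a completion check with help if needed; the fuller review is visit 0 wording.
- A reader might take section 6.2 to say that readings vary with the operator's pressure. The words "specifically if they are used too often or with too much pressure" belong to a safety remark about skin irritation or damage and say nothing about measurement.
- A reader might conclude that every skin endpoint is affected. Section 3.3 does not say how the Visia images are analysed, and section 2.2 presents the skin measurements as objective.
- A reader might call the single-assessor sentence false. It is incomplete: one assessor does reduce one component of measurement error.

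It is also fair to say that section 2.3 openly discloses the lack of blinding, that irregular intake can lead to exclusion under section 3.4, and that the questionnaire carries health and adverse-reaction information that may be wanted before the procedures. The last of these shapes the fix.

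**Conclusion.** The point holds in limited form. At months +1 and +3 the unblinded doctor may know an individual's reported response and adherence before taking the readings, and the single-assessor safeguard does not address the expectation this can create. Without a control arm, the secondary skin endpoints are open to it, most clearly those from hand-applied probes.

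The size is unknown. The rates of 17% and 40% rest on assumed uniform shifts of 0.1 and 0.2 SD and must not be read as the effect of visit order. The conclusion assumes that the completion check or assistance exposes answers to the doctor in at least some cases, and that the doctor's handling can influence a probe reading. The second assumption is plausible but not stated in the protocol. This is a cheap improvement to secondary endpoints and not a flaw in the primary analysis.

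**What to change.** In section 3.3, for months +1 and +3:

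- Take the skin readings before the subjective-change and intake items are discussed or completed with help, and with the participant's earlier readings closed.
- Leave every health, adverse-reaction and skin-safety check where it now stands.
- If any ultrasound or Visia result needs a region marked by hand, have the same doctor mark all images after the last month +3 visit, on coded files in random order without visit labels.
- State that these steps reduce but do not remove expectation bias, because the doctor still knows the visit and that everyone takes the product.
- As a clarification, reword the single-assessor sentence to say that one assessor reduces between-assessor variation.

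The cost is a changed visit flow, with the questionnaire items handled in two parts, the coding of image files, and a delay in any manual image marking until the last month +3 visit. No extra staff, visits or participants are needed.

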- After the determination of biological age, the sequence data is deleted and the saliva samples are destroyed. This minimizes the risks of the data being used in any other way or of personal genetic information being revealed.
- The samples are screened upon arrival at Trume labs and in the case that a sample is contaminated or too wet, we will be informed and ask the participant to retake the saliva sample. As we ship the samples every week, in the case that a sample is contaminated it will be possible for the participant to redo the sample within 1 to 1.5 months maximum considering shipping times. The delay of the datapoint will be taken into account for the analysis.

•

Questionnaire

- The private information provided in the questionnaires will be kept confidential, following our protocol for data protection
- Contact details of trial doctor's are provided to the patients for any case of privacy concerns, mental support or language difficulties

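### Each participant's two saliva samples reach the laboratory about six months apart with no common assay run stated, so a shift between assay periods would be confounded with the primary change

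*Protocol*

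**What the plan says.** **Shipment.** Section 3.3 says of the baseline samples: "The study personnel will collectively ship the samples to Trume labs once all the baseline visits are completed". For month 6 it says: "There the samples will be collectively sent for analysis to Trume labs once all samples from time point +6 have been collected". Section 6.2 has a different rule: "The saliva samples are collectively shipped every week (the samples that are ready) to our collaborator, Trume labs". It repeats the weekly rhythm when it explains how a contaminated or wet sample can be retaken within 1 to 1.5 months.

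**Collection (3.3).** At baseline the participant gives the sample at the clinic under instruction, and staff see to the drying: "The paper has to dry for 45 minutes in the open air (taken care of by the medical professional". At month 6 there is no visit. The participant collects and dries the sample alone, using a kit handed out at month 3, and posts it to the sponsor's site. Two reminders, instructions and telephone support are provided.

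**Stability and destruction.** Section 6.2 says of the samples that "they are stable up to one year under ambient conditions", and later: "After the determination of biological age, the sequence data is deleted and the saliva samples are destroyed". Section 6.1 agrees, and 7.3 has the genetic information deleted promptly once biological age is known. Section 7.4 places destruction of biological material after completion of the study.

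**Design and analysis.** Section 2.3 describes one group without randomisation or placebo, each participant compared with their own baseline, and saliva at months 0 and 6 only. Section 4.1 regresses the reduction in biological age on chronological age and sex, with a one-sided 0.05 level.

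**The concern.** The primary result is a within-person change between two laboratory measurements. In a controlled trial, a difference between assay periods in reagent lot, sequencing run or calibration would affect both arms and largely cancel. Here there is no second arm, so such a difference adds to the estimated change.

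Under the 3.3 shipping rule, consignment and time point coincide for every participant. If each consignment is assayed as it arrives, a batch term would be fully collinear with the change being tested, and no later analysis plan could separate the two. What is at stake is whether a significant result, or a null one, could be attributed to the product at all. The protocol takes care over this for the skin tests, which one doctor performs so as to limit measurement bias. It states no equivalent for the primary endpoint.

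**Working it through.** **1. The two shipping rules side by side.**

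| | Section 3.3 | Section 6.2 |
|---|---|---|
| Baseline samples | One consignment after the last baseline visit | Weekly, as ready |
| Month-6 samples | One consignment after the last sample | Weekly, as ready |
| Gap within a pair | About 6 months | About 6 months |
| Consignment and time point | Identical | Several consignments per time point |

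Weekly shipping breaks up the blocks but does not bring a pair together. By the calendar in 3.3, recruitment starts in August and the latest follow-up visit falls in December or January. If that is the month-3 clinic visit, the last baseline falls around September or October. Month-6 samples from an August start fall around February, so baseline and month-6 consignments would hardly overlap.

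**2. Where a shift goes.** Let the measured reduction be D = true reduction + s + noise, where s is a constant shift between assay periods towards lower measured age. Then mean(D) estimates the true reduction plus s. Sex and chronological age do not vary with time point in a way that could absorb s. Section 2.1 compares with baseline and 4.1 with chronological age. Under either reading s enters one for one, because chronological age advances by a known amount.

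**3. The plan's n.** Inputs from 4.1: one-sided alpha 0.05, power 0.80, effect size 0.5. The two-sample normal formula gives 2 × (1.645 + 0.842)² / 0.5² = 49.5, so 50. Dropout gives 50/0.85 = 58.8, so 59, and 50/0.80 = 62.5, so 63. The stated 50 and 59-63 reproduce, although 50 is the per-group size of a two-sample test. That is a separate matter; 50 is used below only as the evaluable number.

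**4. Illustration of size.** One-sided one-sample t-test of the change, n=50, no true effect. The critical value is t(0.95, 49) = 1.677, so a mean change of 1.677/√50 = 0.237 SD is already significant. With a shift of s SD of the change, the rejection rate is the upper tail of a noncentral t with 49 degrees of freedom and noncentrality s√50. The protocol gives neither the SD of the change nor any shift, so the values of s are assumptions.

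| Shift (SD of change) | Noncentrality | Towards lower age | Towards higher age |
|---|---|---|---|
| 0.1 | 0.71 | 17.2% | 1.0% |
| 0.2 | 1.41 | 40.1% | 0.1% |
| 0.3 | 2.12 | 67.3% | 0.01% |
| 0.5 | 3.54 | 96.7% | below 0.01% |

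In the unfavourable direction, a true effect of 0.5 SD with an opposing shift of 0.3 SD leaves 0.2 SD, and power falls from 96.7% to 40.1%.

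**5. What weekly shipping would change.** A simulation (20,000 repetitions, n=50, no true effect) gave each batch an independent random effect with SD 0.2 of the SD of the change. False positives were about 23% with one batch per time point, 11% with four and 8% with eight. More batches average out random batch error. They do not remove a steady drift or a difference in collection.

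**The case against.** **Shipment is not assay.** A reader might infer from 3.3 that time point and laboratory batch are the same variable. The document does not say so. Section 7.3 lists the laboratory steps without dates, and run layout and controls may sit in a laboratory manual. This stands, and the point is therefore conditional on assay on receipt. The inference is not idle: the month-6 samples are sent for analysis, and no hold is mentioned.

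**A later bridging run is not ruled out.** It is tempting to conclude from 6.2 that the baseline material will be gone. Section 7.4 puts destruction after study completion, so the documents conflict and do not establish this.

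**No shift is shown.** Its existence, size and sign are unknown, and the false-positive rates apply to one direction only. This stands; they illustrate sensitivity and do not predict an error. They also come from a simple test, not from the planned regression with multiplicity adjustment.

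**The collection difference is modest.** Spoon, paper and drying time are the same, collection is self-administered both times, and samples are inspected on arrival. Nothing in the protocol shows that the setting moves a methylation result. A reader should not treat it as an established bias.

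**The remedy has its own confounder.** Under the two-consignment rule, storage ages at assay are broadly similar. With paired assay every baseline card is about six months older than its partner. This stands and is listed as a cost.

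**Conclusion.** The concern holds in conditional form. Sections 3.3 and 6.2 contradict each other on shipping, and under both a pair travels about six months apart with no stated common run or bridging sample. If samples are assayed as they arrive, a shift between assay periods is confounded with the primary change, and the single-group design offers no means of separating it. Under the two-consignment rule no batch term could do so either.

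How much this matters depends on a shift the protocol does not quantify. At n=50, an assumed 0.1 to 0.5 SD towards lower age gives 17% to 97% false positives, and the opposite sign masks a real effect. The documents do not support saying that the primary result will be false. They support saying that it is unprotected against an error which can be prevented cheaply before the first sample is assayed.

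**What to change.** - **Reconcile the text.** Align 3.3 with 6.2 on shipping, and 6.1, 6.2 and 7.3 with 7.4 on when samples and sequence data are destroyed.
- **Ship for receipt and inspection, assay in pairs.** Weekly shipping would preserve the retake window in 6.2. Extraction, bisulfite conversion and sequencing of both of a participant's samples should be done in the same run, in random order within the pair.
- **Mask the time point.** The study team supplies a coded pairing list. Section 7.3, under which the laboratory identifies samples by participant number only, must be amended to match.
- **Keep remaining baseline material and sequence data** until the paired run has passed quality control.
- **Use the same written self-collection instructions** at both time points.

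The cost is an instruction to the laboratory and protocol wording. Later baseline results delay nothing for participants, who receive results only after the study is complete (3.2, 6.1).

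Two downsides should be stated in the protocol. Baseline cards will be about six months older than their partners at assay, so the comparison relies on the stated one-year stability. A baseline sample that passes inspection but fails later can no longer be replaced, and complete-case analysis (4.2) then loses that participant. Pairing removes run-to-run shift only. A collection-setting or other time-related shift remains and should be named as a limitation.
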